1.1 Background

Pemphigus vulgaris (PV) is a very rare chronic autoimmune blistering skin disease caused by autoreactive antibodies that bind to protein components of the desmosome. Within the epidermis, desmosomes play a critical role in maintaining intracellular adhesion between keratinocytes and are important for maintaining the structure and barrier function of skin.

Commercially Confidential Information

. Prior to treatment with corticosteroids, the diagnosis of PV was fatal. However, even with current therapy patients with pemphigus vulgaris have an increased mortality with a hazard ratio for death of 3.38 (95% confidence interval 2.21 to 5.17) after adjustment for sex, calendar period, and age group ([Langan et al 2008](#)).

The current standard of care for patients with moderate to severe PV is immunosuppressive therapy including oral corticosteroids which are commonly paired with another systemic immunosuppressant such as methotrexate, azathioprine, or mycophenolate mofetil ([Feldman and Ahmed 2011](#)). Patients with active disease despite significant therapy or those who are not able to tolerate this therapy are frequently treated with rituximab ‘off-label’ which has demonstrated efficacy in PV patients in multiple clinical studies and case series. B cell depletion with rituximab, an anti-CD20 monoclonal antibody (mAb) approved for the treatment of rheumatoid arthritis and lymphoma among other indications, leads to a ~65% complete response rate in PV patients across various studies. Furthermore, the safety profile of B cell-depleting therapies has been favorable, even in patients with co-morbidities ([Levesque 2009](#)). The dose of rituximab and severity of patient’s disease both appear to influence the complete response rate observed in different studies ([Feldman and Ahmed 2011](#)). After B cell depletion, most patients experience a remission of disease that can last between 6 and 34 months, but nearly all patients eventually relapse or require additional treatment. A recent publication by Colliou et al demonstrated longer lasting remissions, up to six years, in newly diagnosed PV patients who were treated first line with rituximab due to a contraindication to corticosteroid use ([Colliou et al 2013](#)).

Commercially Confidential Information

Commercially Confidential Information

1.1.1 Relevant data summary

Detailed background information on the chemistry, pharmacology, toxicology, preclinical and clinical data of VAY736 is given in the Investigator's Brochure. The data most relevant for the present study is summarized below.

Commercially Confidential Information

Commercially Confidential Information

Commercially Confidential Information

Commercially Confidential Information

1.1.1.3 Human safety and tolerability data

As of 08-May-2013, human clinical experience with VAY736 is primarily limited to Rheumatoid Arthritis (RA) patients (n = 41, 31 treated) of mild-to-moderate disease severity in an ongoing phase I study CVAY736X2101 designed to assess the safety, tolerability, pharmacokinetics ^{Commercially Confidential Information} in single- and multiple-ascending doses of the compound.

Commercially Confidential Information

Commercially Confidential Information

Commercially Confidential Information

1.1.1.5 Human pharmacodynamic data

Clinical experience to date with VAY736 in autoimmunity is limited to the 41 RA patients in the double blind, randomized, phase 1 ascending SD trial (CVAY736X2101) in which each dose cohort contained 3 patients receiving the active compound and one patient receiving a placebo infusion.

Commercially Confidential Information

Commercially Confidential Information

Commercially Confidential Information

1.2 Study purpose

The purpose of the study is to determine if single i.v. doses of VAY736 can reduce disease activity in PV, determined by the change in Pemphigus Disease Area Index (PDAI) as compared to placebo. The study will also provide the first safety and tolerability information for VAY736 in PV patients.

2 Study objectives

2.1 Primary objective(s)

- To compare the efficacy of single i.v. doses of VAY736 relative to placebo in reducing clinical disease activity of pemphigus vulgaris patients, as determined by the change in Pemphigus Disease Area Index (PDAI) between baseline and 12 weeks

2.2 Secondary objective(s)

- To evaluate the safety and tolerability of VAY736 in patients with PV
- To evaluate the effect of VAY736 in PV patients as assessed by the Autoimmune Bullous Skin disease Intensity Score (ABSIS) at 12 weeks
- To evaluate the effect of VAY736 in PV patients as assessed by Investigator Global Assessment (IGA) at 12 weeks
- To evaluate VAY736 pharmacokinetics in serum in PV patients

2.3 Exploratory objective(s)

Commercially Confidential Information

3 Investigational plan

3.1 Study design

This is a non-confirmatory, randomized, partial-blind, placebo-controlled trial evaluating the efficacy, safety, pharmacokinetics of VAY736 in the treatment of patients with pemphigus vulgaris. Commercially Confidential Information

Up to approximately 32 patients will be randomly assigned in a blinded fashion to one of three single dose treatment arms, and at least 24 patients are expected to complete the study. Recruitment will be staggered and progression between doses is dependent upon a safety review milestone (see [Figure 3-1](#)).

[figure not shown]
In the pre-safety review period, 9 patients will be randomized to a single dose of either 3 mg/kg VAY736 or placebo (6 dosed with VAY736 and 3 with placebo). After dosing of these 9 initial patients, recruitment will be paused and a safety review will be conducted by an internal Data Monitoring Committee (DMC), independent from the VAY736 project team (see [Section 8.4](#)).

The DMC will review all safety data available to the 9th patient achieving Week 6. If there are no safety signals identified by this safety review, recruitment will restart into the 3 mg/kg VAY736 and placebo treatment arms, and will commence to the 10 mg/kg VAY736 treatment arm. If there is a safety signal enrollment will be put on hold, pending a full data evaluation.

Following treatment on Day 1 with study medication, standard of care (SoC) medications are to be maintained at a stable dose level with minimal dose adjustments until “disease control” in signs/symptoms of PV. “Disease control” is defined as the time at which new lesions cease to form and established lesions begin to heal (Murrell et al 2008). A protocol-defined SoC medication taper begins once a patient reaches disease control, to safely deliver the patient to the lowest dose needed to maintain control of their disease (see Section 5.5.5).

[figure not shown]
At study completion, it is intended that 9 patients will have been dosed with VAY736 at 3 mg/kg, 9 patients with 10 mg/kg, and 6 patients with placebo.

Figure 3-1 Study design: Staggered recruitment

The study will consist of the following Phases (see Figure 3-2):

Figure 3-2 Study design: Visit Schedule

Key:

B: Baseline; **R:** Randomization; **U:** unblinding of patient treatment; *****: Placebo patients may enter into open-label VAY736 treatment and restart the study at Day 1

Screening Period

The Screening Period consists of a Screening Visit performed within 28 days prior to randomization to assess patient eligibility.

Disease activity will be assessed.

Commercially Confidential Information

If a confirmation of a diagnosis of PV is required, skin biopsies will be taken and assessed locally only where not previously performed and documented as part of the patient's regular medical care.

Baseline/Randomization Visit

Following Screening, patients will undergo pre-dose procedures including completion of patient reported outcomes (including visual analog scale [VAS] for

Commercially Confidential Information

. In addition, blood samples will be taken for the detection of anti-VAY736 antibodies and other pathway related biomarkers. Digital photographs will then be taken (e.g., torso and extremities) to document disease activity.

Patients will then receive the study drug, which will be administered over approximately a 2 hour period. During this time, the patient will be monitored closely with vital signs taken every 30 minutes. In addition, all patients will receive premedication with paracetamol (or acetaminophen) and a H1 receptor blocker to diminish the signs and symptoms of infusion reactions.

The patient will remain in the study center overnight post-infusion for observation and for measurement of safety parameters, PK samples approximately 24 h post-infusion (start of infusion: ± 2 h). Patients will then be discharged from the study site and return as per the schedule described below.

Patients will be given a medication and symptom diary to record any AEs or concomitant medications taken throughout the course of their participation in the study.

No patients shall be infused in parallel at the same time and same center. Treatment of infusion reactions is described under [Section 5.5.7](#).

Double-blind Period

Commercially Confidential Information

A patient may reach “disease control” in their PV between protocol-defined study visits. In such a circumstance, ad-hoc unplanned clinic visits or consultation over the phone is possible to review/alter a patient’s SoC medication dose (see [Section 5.5.5](#)).

Commercially Confidential Information

Open label administration of VAY736 in Placebo patients

After 24 weeks in the study, at the Week 24 visit (or before in case of early withdrawal from the double-blind period that meets certain conditions – see [Section 5.5.8](#)), patients' treatment will be unblinded. When the blind is broken and a patient was assigned to placebo during the double blind period, such a patient will be offered the option to receive open label VAY736 administration from approximately one week after the Week 24 visit, and will follow the same visit pattern as if re-starting from Day 1. Patients will be assigned a new patient number for the open-label treatment. Patients joining the open label part of the study have to satisfy inclusion for active disease and safety labs as mentioned in [Section 4](#), within 2 weeks of their prior Week 24 visit. The dose of VAY736 administered will be 3 mg/kg if a patient reaches Week 24 prior

to the study safety review or 10 mg/kg if dosed after a favorable safety review by the DMC. If a patient prefers not to receive open label active treatment, they are to return within 4 weeks for their EoS visit.

For logistical reasons, it may be necessary for patients to come to the site or a hotel the evening before their scheduled assessment visit, or remain at the site following the visit (e.g. transport restrictions, long travel times from home to site). In these instances, the patients would be hospitalized at the site, but this would not be considered as an SAE.

3.2 Rationale of study design

A randomized, placebo-controlled, partial-blind approach is used to eliminate potential bias in reporting safety and biological activity data in this study. The study will be blinded to patients, investigator site staff and the clinical trial team at the time of randomization. Unblinding of patients as they reach the end of double-blind treatment period is planned. This together with the effect of VAY736 on certain assessments may lead to members of the clinical trial team becoming inadvertently unblinded towards the end of the study period.

In addition, the study includes a staggered enrollment to allow progression between the 3 mg/kg and 10 mg/kg to be dependent upon a safety review milestone. The initial 9 patients dosed prior to the safety review will include only the 3 mg/kg VAY736 (n=6) dose and placebo patients (n=3). The rationale for this lower dose group is to confirm that the safety profile in patients with PV with regard to infusion reactions and other short term safety parameters (e.g. chemistry and hematology) is favorable, similar to that observed in study CVAY736X2101. A favorable safety review by the DMC will then enable randomization to commence into the 10 mg/kg dose group and completion of the remaining 3 mg/kg and placebo groups.

In the event that efficacy is observed with both 3 mg/kg and 10 mg/kg, the relationship between dose and parameters of clinical response (e.g., time to remission, duration of remission) can be better explored with a range of doses and exposures offered by these two dose groups.

3.3 Rationale of dose/regimen, duration of treatment

Ten (10) mg/kg is the target dose proposed to test efficacy of VAY736 in PV patients in this single i.v. dose study. This dose was safe and well tolerated in the recently completed single dose part of the 3-fold sequential dose escalation phase I study (CVAY736X2101; dose range 0.0003 mg/kg to 10 mg/kg) where it was the maximum VAY736 intended dose administered to RA patients.

Commercially Confidential Information

A 3 mg/kg dose will also be tested in the study. The purpose of this lower dose group is to explore a range of drug exposures and provide early dose ranging to understand better the relationship between PK,

Commercially Confidential Information

3.4 Rationale for choice of comparator

In the current study, placebo will be used as a comparator to provide objective evidence of potential AEs and other safety data, as well as clinical efficacy data generated from patients exposed to the experimental therapy.

The risk of a patient experiencing uncontrolled disease is minimized by continuous use of SoC medication (including azathioprine and mycophenolate mofetil). Furthermore, after unblinding, patients initially randomized to placebo will be offered optional treatment with a single administration of VAY736. The purpose of this optional open label administration of VAY736 is to allow all patients who participate in this study to have an equitable chance to eventually receive study drug.

An active comparator is not included in this study.

3.5 Purpose and timing of interim analyses/design adaptations

Commercially Confidential Information

3.6 Risks and benefits

Commercially Confidential Information

Patients treated with VAY736 will experience suppression of a part of their immune system and this carries a theoretical risk of increased infections. In this study, patients with PV will also be exposed to other immunosuppressant agents which are the current standard of care for PV. As patients are required to have PV disease activity to be enrolled in this study, they have a medical need for further treatment in order to suppress their disease. The risk to patients from exposure to multiple immunosuppressant agents will be minimized by a protocol required tapering of these SoC treatments as allowed by their clinical response. Additionally, patients will comply with local requirements for infection prophylaxis (e.g. *Pneumocystis carinii*) that are appropriate for patients on multiple immunosuppressants including B cell suppression.

Other potential risks must be considered with administering VAY736 in humans.

Commercially Confidential Information

In addition, hypersensitivity and anaphylaxis are potential risks associated with mAbs.

Patients will be required to have skin sampling by punch biopsy. This procedure is commonly performed in dermatology practice and when performed by a trained medical practitioner carries a minimal risk of infection and bleeding. Minor discomfort and a scar at the site of the biopsy should be expected.

3.6.1 Risks associated with immunosuppressants in general

3.6.1.1 Infection

Excessive down-regulation of critical components of the immune system will increase susceptibility to infection. This risk is related to intensity and duration of the immunosuppressive regimen.

Commercially Confidential Information

Infections developing in patients exposed to VAY736 should be promptly diagnosed and appropriately treated.

3.6.1.2 Vaccinations

There is currently no data on the influence of VAY736 on response to vaccines in general. Vaccination success may be attenuated under immunosuppressive therapy. It is recommended that, if possible and taking in account the overall status of the patient, potential study participants should complete all pre-planned immunizations in accordance with current immunization guidelines prior to exposure to VAY736.

3.6.2 Potential Risks associated with VAY736

3.6.2.1 Late onset neutropenia

Commercially Confidential Information

LON has been reported infrequently in association with rheumatologic diseases, with an incidence between 3% and 27% ([Wolach et al 2012](#); [Tesfa and Palmblad 2011](#)) and has been associated with treatment of PV ([Rios-Fernández et al 2007](#)). LON in patients with rheumatic diseases typically self-resolve rapidly and infrequently results in serious infections. The specific cause of late onset neutropenia remains unknown and rechallenge with rituximab has not led to recurrent neutropenia in previously affected patients.

Commercially Confidential Information

3.6.2.2 Potential immune-mediated reactions

3.6.2.2.1 Hypersensitivity reactions

The main safety concerns with use of mAbs typically include intolerance

Commercially Confidential Information

In addition, excipients in the formulation are present. Either has the potential to result in a hypersensitivity reaction to the formulation. This may clinically manifest in the following ways: acute or delayed allergic reaction, anaphylaxis (very rarely), urticaria, rash, dyspnea and/or hypotension, fever, and chills. VAY736 is a fully human mAb of the IgG1 class. This class of antibody is normally abundant in humans. Therefore, the antibody itself is expected to be less immunogenic in humans than chimeric or humanized antibodies. Assays to detect a putative antibody response to VAY736 are included in the study design.

Serum sickness is a delayed reaction (generally over 4–10 days) to serum proteins or monoclonal antibodies, consisting of a hypersensitivity reaction with immune-complex generation and vascular damage in the skin, joints and kidneys. It occurs especially with chimeric antibody, and its likelihood remains very low for fully human monoclonal antibody.

3.6.2.2.2 Infusions reactions and cytokine release

Commercially Confidential Information

Infusion reactions have been experienced by over a third of RA patients exposed to rituximab, with the majority of cases occurring during first exposure when the target cell population is at relatively high levels. Clinical studies with rituximab in PV patients suggest a similar frequency with most reactions being mild and transient ([Joly et al 2007](#)). Infusion reactions experienced by RA patients receiving VAY736 as a single intravenous dose up to 10 mg/kg have been limited to mild-to-moderate severity. These reactions occurred in the absence of pre-medication and the resulting signs and symptoms were responsive to treatment with paracetamol.

In the event of an infusion reaction requiring treatment, there should be ready access to intravenous fluids, glucocorticoids, anti-histamines, and acetaminophen as required by the patient's condition. Advanced life support units should also be rapidly accessible within the same facility. In addition, plasmapheresis may be helpful in situations in which decreasing the systemic concentration of VAY736 may be of clinical benefit, based on capacity of plasmapheresis to remove IgG antibody, such as the IgG monoclonal antibody VAY736, from intra- and extra-vascular compartments.

3.6.3 Potential Risks associated with SoC medication

3.6.4 Corticosteroids

Patients will be allowed to continue to use oral corticosteroids. Corticosteroids are a standard of care treatment for patients with PV. Although commonly used, corticosteroids are hormones and have a risk of systemic adverse events which include, but are not limited to, suppression of adrenal gland function, skin thinning, weight gain, bone weakening, increased risk of infection, and worsening of diabetes among others. The deleterious impact of systemic corticosteroid use on patients with PV has been documented and the risk will be minimized by tapering the steroids if patients are experiencing control of their disease ([Mahajan et al 2005](#)).

3.6.5 Azathioprine

Patients will be allowed to continue to use azathioprine. Azathioprine is a standard of care treatment for patients with PV and has a risk of adverse effects that includes a risk of cytopenias (e.g., thrombocytopenia, leukopenia, anemia and/or pancytopenia), infections, and gastrointestinal hypersensitivity. These adverse effects can be increased in patients who are sensitized due to low levels of TPMT (thioprine S-methyltransferase) activity. Adverse effects of patients on azathioprine are minimized by testing for TPMT as per standard clinical practice. Patients will be required to follow local prescribing information where applicable and local standards of practice for the use of azathioprine as well as careful monitoring for hematologic toxicity.

3.6.5.1 Mycophenolate mofetil (MMF)

Patients will be allowed to continue to use mycophenolate mofetil (MMF). MMF is a standard of care treatment for patients with PV and has a risk of adverse effects that includes a risk of neutropenia, pure red cell aplasia, gastrointestinal bleeding and infections. Adverse effects of patients on MMF will be minimized by following local prescribing information where applicable and local standards of practice for the use of azathioprine as well as careful monitoring for hematologic toxicity.

4 Population

The study population will be comprised of male and female PV patients.

It is planned that up to approximately 32 patients may be enrolled (randomized) into the study; at least 24 patients are expected to complete the study.

The investigator must ensure that all subjects being considered for the study meet the following eligibility criteria. No additional criteria should be applied by the investigator, in order that the study population will be representative of all eligible subjects.

Subject selection is to be established by checking through all inclusion/exclusion criteria. A relevant record (e.g. checklist) of the eligibility criteria must be stored with the source documentation at the study site.

Deviation from **any** entry criterion excludes a subject from enrollment into the study.

4.1 Inclusion criteria

All patients

Patients eligible for inclusion in this study have to fulfill **all** of the following criteria:

1. Written informed consent must be obtained before any assessment is performed.
2. Male and female patients 20 to 70 years of age inclusive (at the time of the Screening visit), and having passed Screening examinations by past medical history, physical examination, vital signs, electrocardiogram, and laboratory tests.
3. Diagnosis of PV according to (i) presence of blisters or erosions of the skin or mucous membranes, plus (ii) characteristic documented histological findings in the skin, plus (iii) characteristic findings from direct immunofluorescence in skin

Commercially Confidential Information

If results are not available, biopsies and a blood sample have to be taken at screening to confirm diagnosis.

4. Presence of mild to moderate active PV at Baseline as defined by a PDAI score between 20 and 60 (inclusive) or for a PDAI below 20: an IGA of 2 to 3 (e.g., at least 1% but not more than 10 % BSA involvement).

5. On a stable dose(s) of oral corticosteroid +/- adjuvant therapy of azathioprine or mycophenolate mofetil. Requirements for these standard-of-care (SoC) medications are:
 - Oral corticosteroids alone, with steroid dose to be equivalent to prednisone ≥ 15 mg per day but no greater than 2 mg/kg/day; or
 - Oral corticosteroid + azathioprine, with steroid dose to be equivalent to prednisone ≥ 2.5 mg per day but no greater than 1 mg/kg/day, and azathioprine with no specific daily dose requirement; or
 - Oral corticosteroid + mycophenolate mofetil, with steroid dose to be equivalent to prednisone ≥ 2.5 mg per day but no greater than 1 mg/kg/day, and mycophenolate mofetil with no specific daily dose requirement.
6. SoC medications considered stable if the daily dose has not changed within the 7 days preceding the day of dosing (Day 1) for oral corticosteroid, or within the 14 days preceding the day of dosing (Day 1) for azathioprine and mycophenolate mofetil. Patients must weigh in the range of 40 kg to 150 kg inclusive.
7. Able to communicate well with the investigator, to understand and comply with the requirements of the study.

Open-label patients (i.e. for placebo-treated patients)

1. Presence of mild to moderate active PV at unblinding, as defined by a PDAI score more than 10.
2. On a stable dose(s) of oral corticosteroid +/- adjuvant therapy of azathioprine or mycophenolate mofetil. Requirements for these SoC medications are:
 - Oral corticosteroids alone, with steroid dose to be equivalent to prednisone ≥ 15 mg per day but no greater than 2 mg/kg/day; or
 - Oral corticosteroid + azathioprine, with steroid dose to be equivalent to prednisone ≥ 2.5 mg per day but no greater than 1 mg/kg/day, and azathioprine with no specific daily dose requirement; or
 - Oral corticosteroid + mycophenolate mofetil, with steroid dose to be equivalent to prednisone ≥ 2.5 mg per day but no greater than 1 mg/kg/day, and mycophenolate mofetil with no specific daily dose requirement.

SoC medications considered stable if the daily dose has not changed within the 7 days preceding the day of dosing (Day 1) for oral corticosteroid, or within the 14 days preceding the day of dosing (Day 1) for azathioprine and mycophenolate mofetil.

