6.4 Efficacy / Pharmacodynamic assessments

6.4.1 Pemphigus Disease Area Index (PDAI)

The PDAI is a specific cutaneous and mucosal disease activity assessment performed by the investigator based on the evaluation of lesions in well-defined anatomical locations ([Pfützte et al 2007](#); [Murrell et al 2008](#); [Rosenbach et al 2009](#); [Daniel et al 2012](#)).

The score is weighted for the number and size of lesions with a score of 0 (absent) to 10 given for skin (12 body locations), scalp and mucous membrane showing disease activity (erosions/blisters or new erythema). To be more precise at the lower end of the PDAI score the value of 1 that included 1-3 lesions on each anatomic region is split in intervals: 1 corresponds to one lesion (none greater than 2 cm); 1.3 corresponds to two lesions and 1.6 corresponds to three lesions.

Damage, such as post inflammatory hyperpigmentation or erythema from resolving lesion, is scored separately from the main score as absent (0) or present (1) for each body area or scalp resulting in a score of 0 to 12 or 0 to 1, respectively.

Therefore the PDAI score ranges from 0 to 263, with 250 points representing disease activity (120 points for skin activity; 10 points for scalp activity; 120 points for mucosal activity) and 13 points representing disease damage. Please refer to the PDAI scoring sheet in [Section 18-Appendix 6](#).

The investigator will complete a paper copy of the scale, which will serve as source data and the subject's responses will be transcribed into the CRF.

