9.4.1 Variable(s)

The primary efficacy variable is the PDAI skin and mucous membranes activity score (i.e. the sum of the skin activity sub-score and mucous membranes activity sub-score of the PDAI) recorded at baseline and weeks 3, 6, 9, 12, 16, 20 and 24.

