1	in one quadrant		1	present																											
2	two quadrants																														
3	three quadrants																														
4	affects whole skull																														
10	at least one lesion >6 cm																														
Total Scalp	/10	/1																													

Mucous membrane

Anatomical location	Erosion/Blister	
	0 absent 1 1 lesions 2 2-3 lesions 5 >3 lesions or 2 lesions >2 cm 10 entire area	Number lesions if ≤3
Eyes		
Nose		
Buccal mucosa		
Hard palate		
Soft palate		
Upper gingiva		
Lower gingiva		
Tongue		
Floor of mouth		
Labial bucosa		
Posterior pharynx		
Anogenital		
Total Mucosa	/120	

Total Activity Score

= Total Skin Activity Score + Total Scalp Activity Score + Total Mucosa Activity Score

[figure not shown]
Total Damage Score

= Total Skin Damage Score + Total Scalp Damage Score

PDAI Score

= Total Activity Score + Total Damage Score

19 Appendix 7: Assessment of Body Surface Area

Head & neck:	9%	Arm incl hand:	9%
Trunk (front & back)	36%	Leg:	18%
Genitals:	1%	Palm of the hand (including fingers):	1%

20 Appendix 8: ABSIS scoring sheet

ABSIS SCORING SHEET

Date: _____
Patient's weight
(kg): _____

Skin Involvement (Max BSA)	Patient's BSA	Weighting Factor	% BSA x Weighting Factor
Head & neck (9%)			
L Arm including hand (9%)			
R Arm including hand (9%)			
Trunk (front & back) (36%)			
L Leg (18%)			
R Leg (18%)			
Genitals (1%)			
			Total Score ¹ _____

¹Skin Involvement Total Score ranges from 0 – 150 points

Legend for weighting factor (most dominant appearance of skin lesions):	
1.5	Erosive, exudative lesions
1.0	Erosive, dry lesions
0.5	Reepithelialized lesions (incl. post inflammatory erythema and/or hyperpigmentation)

I. Oral Extent (enter 1 for presence of lesions, 0 absence of any lesion):

Upper gingival mucosa	
Lower gingival mucosa	
Upper lip mucosa	
Lower lip mucosa	
Left buccal mucosa	
Right buccal mucosa	
Tongue	
Floor of the mouth	
Hard palate	
Soft palate	
Pharynx	
	Total Score ² _____

²Oral Total Score ranges from 0-11

II. **Severity** (Subject discomfort during eating/drinking)

Food, e.g.	Level	Factor of Discomfort	Level x Factor of Discomfort
Water	1		
Soup	2		
Yogurt	3		
Custard	4		
Mashed potatoes/scrambled egg	5		
Baked fish	6		
White bread	7		
Apple/ raw carrot	8		
Fried steak/ whole-grain bread	9		
			Total Score ³ _____

³Total Severity Score ranges from 0-45

Legend for Factor of Discomfort	
1	Pain/bleeding occurred always

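### Both eligibility criteria define active disease by a PDAI score that includes up to 13 damage points, so damage can bypass the IGA check at entry and can alone meet the open-label activity criterion

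*Protocol*

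**What the plan says.** **Entry.** Protocol Section 4.1, criterion 4, requires mild to moderate active disease at baseline, "as defined by a PDAI score between 20 and 60 (inclusive"), "or for a PDAI below 20: an IGA of 2 to 3". The 20 to 60 route carries no IGA condition. The route below 20 carries one but has no PDAI minimum.

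**Open-label part.** Criterion 1 for placebo patients reads "Presence of mild to moderate active PV at unblinding, as defined by a PDAI score more than 10". It has no IGA condition.

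**The score.** Section 6.4.1 states: "Therefore the PDAI score ranges from 0 to 263, with 250 points representing disease activity". The other 13 points are damage: post-inflammatory pigmentation or erythema of resolving lesions, one point for each of 12 skin areas and one for the scalp. The scoring sheet in Appendix 6 computes the PDAI score as "Total Activity Score + Total Damage Score" and also totals activity on its own line.

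**The primary variable.** Protocol Section 9.4.1 defines it as "the sum of the skin activity sub-score and mucous membranes activity sub-score of the PDAI". The PDAI total is a separate secondary variable (Section 9.5). SAP Section 7.1.1 names the same skin and mucosal score but labels it the PDAI score, lists scalp among the scored sites and repeats the 0 to 263 range.

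**Related statements.** Sections 4 and 4.2 bar investigators from adding eligibility criteria of their own. The benefit-risk argument in Section 3.6 rests on enrolled patients having disease activity.

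**The concern.** Damage points mark where lesions have been. A criterion headed as active disease should not be met, or failed, because of them. Taken at the definition in 6.4.1 and Appendix 6, both criteria allow this.

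Three things are at stake:

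- **The IGA check at entry.** It is the only safeguard on the extent of active disease for patients with a low score. Damage points can move a patient into the route where it does not apply, and a site may not add a check of its own.
- **The open-label offer.** A placebo patient could meet the disease-activity criterion for open-label VAY736 with no active lesion. That conflicts with the criterion's own heading and with the premise in Section 3.6.
- **The primary comparison.** Patients admitted on damage points start with a lower score on the primary variable than their entry score suggests, while the success rule is an absolute difference of 10 points.

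**Working it through.** **Inputs.** Skin activity 120, scalp activity 10, mucosal activity 120, damage 12 + 1 (Protocol 6.4.1, Appendix 6). Entry limits 20 and 60, open-label limit above 10 (4.1). Success rule (synopsis, data analysis): at least a 10-point difference with 50% evidence, and a difference above zero with 90% evidence. Design: 9 versus 6 patients, SD 8, true difference 14 (9.6).

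**1. The stated range reproduces.** 120 + 10 + 120 = 250 and 12 + 1 = 13, so the total is 263. The primary variable in 9.4.1 has a maximum of 120 + 120 = 240. The points outside it are 10 (scalp) + 13 (damage) = 23.

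**2. Lower limit.** Least activity at PDAI 20 = 20 − 13 = 7. With an activity-only score the same patient has 7, falls below 20 and must show an IGA of 2 to 3.

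**3. Upper limit.** Activity 60 with one damage area gives 60 + 1 = 61, which is excluded. With all 13 damage areas, any activity above 60 − 13 = 47 is excluded.

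**4. Open-label limit.** Activity 0 + damage 11, 12 or 13 gives 11, 12 or 13, each above 10.

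**5. Room to improve on the primary variable, 20 to 60 route.**

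| Lowest possible baseline at the entry limit of 20 | Present rule | Total Activity rule |
|---|---|---|
| Scalp not in the primary variable (Protocol 9.4.1) | max(0, 20 − 23) = 0 | 20 − 10 = 10 |
| Scalp counted (one reading of SAP 7.1.1) | 20 − 13 = 7 | 20 |

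The zero needs a scalp score of 10, which is an active lesion over 6 cm, plus damage in at least 10 areas. The next scalp level is 4, and 13 + 4 = 17 does not reach 20.

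**6. The plan's operating characteristics.** With a flat prior and known SD, SE = 8 × √(1/9 + 1/6) = 4.216. The 90% criterion needs 1.2816 × 4.216 = 5.40, so the 10-point criterion governs. Chance of success = 1 − Φ((10 − true difference)/4.216).

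- True difference 0: 0.89% (plan: below 1%).
- True difference 6: 17.1% (plan: below 20%).
- True difference 14: 82.9% (plan: about 80%).

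**7. Illustration of dilution (assumed, not in the documents).** Suppose k of the 9 treated patients gain only c points over placebo and the others gain 14, with SD still 8. The mean difference is (14 × (9 − k) + c × k)/9.

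| k | c = 7: mean, chance | c = 0: mean, chance |
|---|---|---|
| 1 | 13.2, 78% | 12.4, 72% |
| 2 | 12.4, 72% | 10.9, 58% |
| 3 | 11.7, 65% | 9.3, 44% |

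The column c = 7 matches the 7-point patient in step 2 if comparable placebo patients do not change. The column c = 0 needs the rare combination in step 5.

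**The case against.** **The criteria may mean activity only.** Section 6.4.1 also treats damage as separate from the main score, and both criteria are headed as active disease. That reading is available. But the same section and the scoring sheet give the PDAI score as the sum, and the criteria do not say which score applies. Two sites could score one patient differently, so the wording still needs settling.

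**Low scores are a deliberate choice.** The route below 20 admits them openly. This stands: that route is a more direct source of little room to improve, and naming the activity score leaves it in place. However, it is gated by IGA, and damage points avoid that gate.

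**The diagnosis criterion already requires lesions.** Criterion 3 asks for "presence of blisters or erosions of the skin or mucous membranes", but sets no minimum extent. For open-label entry, Section 3.1 asks only for active disease and safety laboratory values.

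**Open-label entry has a second gate.** Patients must be on stable standard of care at a minimum steroid dose. A healed patient on steroid alone, tapering under Section 5.5.5, would often miss it. The lower steroid minimum with an adjuvant keeps the case open, so it is narrowed but not removed.

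**Stronger readings that a reader might infer, and that the documents do not support:**

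- *Patients can routinely enter with nothing to improve.* Damage alone cannot reach 20. A primary score of 0 is possible only at PDAI 20 to 23 with the maximum scalp score. That scalp disease is active and can improve, and it counts in the secondary PDAI total.
- *A patient with 10 points at baseline cannot add more than 10 over placebo.* The cap is on that patient's own change. Treated 10 to 0 against placebo 10 to 15 is a 15-point difference.
- *A patient who entered at PDAI 8 and is unchanged at Week 24 shows a contradiction with Section 3.4.* That section aims to "allow all patients who participate in this study to have an equitable chance to eventually receive study drug", but Section 3.1 makes the offer conditional on active disease and laboratory values. The case has nothing to do with damage points.

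**Conclusion.** The point holds as a defect in how active disease is defined. Up to 13 damage points count toward both criteria. They can bring in a patient with as few as 7 activity points without the IGA check, exclude a patient with activity between 47 and 60, and satisfy the open-label activity criterion with no active lesion. These bounds are exact arithmetic on the definition in 6.4.1 and Appendix 6, and fall away only if sites read the score as activity alone.

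The effect on the primary comparison is real in direction but unknown in size. No baseline distribution is given, so the percentages in the illustration show sensitivity and are not a forecast. The open-label issue concerns eligibility only, because that part does not feed the Week 12 comparison.

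Whether scalp is excluded from the primary variable cannot be settled from the two documents together. Protocol 9.4.1 excludes it by omission, and SAP 7.1.1 leaves it unclear.

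**What to change.** 1. In criterion 4 and the matching synopsis text, replace the PDAI score by the PDAI Total Activity Score (skin, scalp and mucosa). Appendix 6 already totals it. Patients who then fall below 20 can still enter through the IGA route.
2. For the open-label criterion, reconcile the heading of active disease and the premise in Section 3.6 with a score that damage alone can satisfy. No threshold is proposed here.
3. Define the primary variable in the same words in Protocol 9.4.1 and SAP 7.1.1, say whether scalp counts, and remove the PDAI score label and the 0 to 263 range from the SAP definition.

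**Cost.** A wording amendment to the protocol and a revision of the SAP text, with no new assessment. A few patients near 20 or 60 would change entry route or eligibility. The change reduces dilution of the primary comparison but does not remove it, because the IGA route still has no PDAI minimum.
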